1.2. Study Schematic

Figure 1 Study Schematic

Abbreviations: CR=complete remission; HSCT=hematopoietic stem cell transplant; SoC=standard of care

- ^a Safety Lead-in (Cohorts I and II) and Cohorts III-V defined as patients who fit a majority of the criteria for Group 2 only (as determined by the Sponsor).
- *Patients in Groups 1 and 2 will receive 100 x 10⁶ cells, but the Sponsor may change the Phase 2 dose regimen to either a higher dose (Cohort III) and/or to the product manufactured using the accelerated process (Cohorts IV and V).

Notes:

- Disease assessment and group assignment occur at Day 80 post-HSCT (±5 days) for Group 1 patients.
- Patients in Group 1 Arm B who relapse after randomization may cross over to Group 2 to receive MT-401 if the particular subgroup is open and/or Sponsor agreement.
- Patients may be identified post-HSCT and enter Group 2 if the same donor cell is available to provide cells for manufacturing MT-401 and eligibility is fulfilled.
- If relapse occurs less than 80 days post-HSCT and T cells have been manufactured and stored, the patient may receive MT-401 and be included in a subgroup analysis of Group 2.
- Group 2 patients may receive MT-401 even if CR_{MRD} is achieved post-bridging therapy but will be analyzed separately.

Confidential Page 17 of 74

1.3. MT-401 Schedule of Activities

Table 1: Schedule of Activities

Procedure	Screening a	Baselineb	Intervention Period and Follow-up [Weeks] ^c						
			0 ^d	2 ^d	4 ^d	Follow-up	Visits ^e		
						12 (±1 week	24 (±1 week	52 (±4 weeks)	Yearly (±4 weeks)
Informed consent	X	X							
Inclusion and exclusion criteria	X	X							
Demography	X								
Medical History and Complete Physical Exam (includes performance status)	X	X							
Brief Physical Exam ^f			X	X	X	X	X	X	X
Pregnancy test (WOCBP only) (serum or urine) ^g	X	X							1
Laboratory assessmentsh	X	X	X	X	X	X	X	X	X
Vital signs ⁱ	X	X	X	X	X	X	X	X	X
Randomization for Group 1 patients ^b		X							
Disease Assessment	X	X	X^k			X	X	X	X
GVHD Assessments		X	X	X	X	X	X	X	X
Study treatment			X	X	X				
AE, SAE, and concomitant medication review		X	X	X	X	←		•	
Biomarkers ⁿ			X			X	X	X	X
PRO questionnaire (Group 2 Subgroup C only) ^o	X	X				X	X	X	X

Abbreviations: AE=adverse event; CBC=complete blood count; eCRF=electronic case report form; GVHD=graft-versus-host disease; HSCT=hematopoietic stem cell transplant; MRD=minimal residual disease; PRO=patient-reported outcome; SAE=serious adverse event; SoA=Schedule of Activities; SoC=standard of care; WOCBP=women of childbearing potential Note: Additionally, treatment visits may be modified for 1 week due to inclement weather, vacation, etc., but any longer durations need to be discussed with the Sponsor. Any unscheduled visit, including discontinuation visits, will follow the assessments shown for Week 24.

Page 18 of 74

^a Screening is to be performed up to 45 days before allogeneic-HSCT or at the time of consideration for study.

^b Baseline for Group 2 patients should be performed within 14 days prior to first infusion. Disease assessment occurs at Day 80 (±5 days) post-HCST, prior to randomization for Group 1 patients.

c Intervention Period includes study treatment and Active Follow-up and Survival Follow-up as defined in Section 4.4 (including for Safety Lead-in portion of the study). Day 0/Week 0 is considered the day of the first infusion of MT-401 (which differs from the Day 1 used for allogeneic HSCT). Each infusion and visit must be at least 2 weeks apart. Active Follow-up Period as defined in Section 4.4: occurs after the last dose of MT-401 has been administered until patient relapses/progresses or declines additional study visits. Timing of Follow-up Visits are in relation to the timing of the Day 0 visit. Sponsor will schedule Day 0 timing for all patients in all groups, including Group 1 SoC arm.

d SoC patients do not need to perform visit Weeks 2 or 4, unless clinically indicated. Week 0 visit for SoC patients may occur between days 85-130 post-HSCT, as instructed by Sponsor.

^e Survival follow-up begins after relapse/progression or active follow-up is completed and occurs every 3 months for 3 years, every 6 months for the remainder of the study (which can be phone contact to collect patient survival status [if alive, last date known alive, and if dead, date of death], and collect any additional anticancer therapy post-MT-401 or SoC received during study.

Confidential Page 19 of 74

f Brief physical exam, to include at a minimum, assessments of the Cardiovascular, Respiratory, and Gastrointestinal systems (height and weight will be needed at screening at minimum and any changes recorded if >10%).

g Pregnancy testing is required unless a patient has no possibility of being pregnant (for example post-hysterectomy). Perform as clinically indicated during intervention period for WOCBP. See Section 8.3.5 for details.

^h On day of MT-401 administration, laboratory assessments and/or disease assessments are completed prior to infusion (see Section 8.2.3 for additional details of laboratory assessments to be performed).

¹ Vital signs obtained within 1 hour pre- and post-infusion (window ± 15 min).

^j Disease assessment will be performed on blood, bone marrow samples, and/or other tissue samples at these time-points. For Group 1 and Group 2, the screening disease assessment may be performed as part of SoC (prior to consent if it was already completed). For Group 1, pre-transplant testing of MRD should be performed locally by any testing methodology and results recorded in the eCRF. Post-transplant baseline MRD testing will be performed centrally, and results must be available prior to randomization. If any additional disease assessments, such as additional time points or additional testing (e.g., imaging for extramedullary disease), or visits occur due to clinical necessity, information will be recorded on eCRF. Includes central testing for MRD status for all samples collected as per SoC and as per standard institutional guidelines at other time points by methods outlined in protocol in Section 4.1 (samples stored for central confirmation at later date). If imaging is performed on a patient, the Sponsor may request imaging to be sent to a central vendor along with any disease assessment reports.

Disease assessment at Day 0 for Group 1 only (disease assessment does not need to be repeated if within 3 weeks of prior disease assessment and results can be pending prior to treatment).

Study treatment is administered for all patients (except SoC - Group 1- Arm B) on Day 0 and every 2 weeks for a planned maximum of 3 doses. Patients randomized to SoC (Group 1B) at 80 days post-transplant may crossover to the relapse group (Group 2) if the patient is found to have relapse of disease (MRD* or frank relapse) and the subgroup is open and/or Sponsor agreement. After relapse and prior to bridging chemotherapy, the patient should perform assessments associated with the Screening visit if not already completed. The patient should perform the assessments associated with Baseline following bridging chemotherapy and prior to MT-401 administration. The patient will have their visits reset and have their MT-401 administered on Day 0 and follow the schedule of events from that point forward. Group 1- Arm B (SoC) patients will continue to follow the SoA minus administration of MT-401. Refer to Section 6 for additional dosing details. Administration of MT-401 can be delayed due to management of AEs or other toxicities, but patients should resume T cell infusions within 2 weeks of their scheduled dose. If greater than 2 weeks is needed, Sponsor will determine if patient can resume T cells infusions.

m All AEs and SAEs, from Day 0 and Baseline, respectively, to the Week 12 Visit will be collected; after Week 12, only treatment-related AEs and SAEs will be collected.

ⁿ Detailed studies outlined in Section 8.8.

o Additional details regarding the PRO questionnaire and associated instructions will be provided in a separate document.

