5.1. Patient Inclusion Criteria

All applicable inclusion and exclusion criteria must be met at Screening (up to 28 days before allogeneic HSCT for Group 1 patients, and prior to the start of manufacturing for Group 2 patients, or at the time of consideration for study) and at Baseline (re-assessment of eligibility within 14 days prior to group assignment for Group 1).

Patients are eligible to be included in the study only if all of the following criteria apply and the patient, in the judgement of the investigator, is an appropriate candidate for experimental therapy:

- 2. Eligible to receive donor-derived MT-401 following first allogeneic HSCT, are in ≤ third complete remission (CR3) prior to transplant (including matched sibling, matched unrelated donor with at least 6 of 8 HLA markers, or haploidentical with at least 5 of 10 HLA markers) as:
 - Adjuvant therapy for AML (**Group 1**) at 85-130 days post-HSCT defined as:
 - patients with CR_{MRD}- by central testing for purposes of randomization (if optional local MRD testing performed and results are positive, the patient will be moved to Group 2 subgroup D);
 - and are considered intermediate/high risk (e.g., pre-transplant MRD+, intermediate/adverse risk cytogenetics or received non-myeloablative or reduced intensity conditioning); or
 - Treatment for relapsed AML (first relapse post-HSCT) when disease occurs after transplant (Group 2) defined as
 - First relapse (MRD+ or frank relapse) post-HSCT
 - Patients in Group 1 who are randomized to Arm B (SoC) and experience first relapse (MRD⁺ or frank relapse) post-HSCT or experience relapse prior to randomization
 - Patients with frank relapse will enter into Subgroup C while patients with MRD⁺ disease will enter into Subgroup D
 - Safety Lead-in (Cohorts I and II) and Cohorts III-V defined as patients whose prior treatment course does not meet precise eligibility criteria but may still be approved upon review by the Sponsor as described above for Group 2 only

Note: Engraftment must be confirmed post-transplant (absolute neutrophil count $> 1000/\text{m}^3$ without granulocyte colony-stimulating factor for 7 days, donor chimerism $\ge 50\%$).

- 2. Are ≥18 years of age prior to administration of MT-401
- 3. Patients must have donor-derived cells available to make MT-401

Confidential Page 34 of 74

- 4. Karnofsky/Lansky score of ≥60
- 5. Life expectancy ≥ 12 weeks
- 6. Adequate blood, liver, and renal function

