6.3. Randomization

Disease assessment and group assignment occur at Day 80 ± 0 (± 5 days) post-HCST, prior to randomization for Group 1 patients. Post-transplant baseline MRD testing will be performed centrally, and results must be available prior to randomization.

For Group 1, randomization codes will be prepared to allow the clinical study sites to enroll patients by using an interactive response technology (IRT) system. Treatment group assignments will be known to site personnel (i.e., investigator, pharmacist, and study staff) and patients. After completion of required screening procedures, patients will be assigned, using the randomization schedule, to MT-401 vs observation (SoC) with a 1:1 allocation. The randomization schedule will be created with two stratification factors as specified in Section 4.1 using random block sizes. SoC patients in Group 1-Arm B who relapse after randomization may cross over to Group 2 to receive MT-401, if the subgroup is open and/or Sponsor agreement.

For Group 2, after the patient's eligibility is established and informed consent has been obtained, the patient will be enrolled, and a number will be assigned through the IRT. Since this is a single-arm cohort, all enrolled patients who meet eligibility criteria will be treated with MT-401.

Due to the nature of the administration of MT-401 along with the fact that the endpoints are objectively evaluated without the concern for bias, the study is not blinded.

Patients in the Safety Lead-in (Cohorts I and II) and Cohorts III-V will not be randomized.

Confidential Page 39 of 74

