9.3.1. Primary Safety Analysis: Safety Lead-In (Cohorts I and II) and Cohort III-V

The primary objectives for the Safety Lead-in are to assess safety and tolerability of MT-401 manufactured using peptides produced by two different vendors, including identifying DLTs. The primary objective for Cohort III is to assess the safety and tolerability of a higher dose than the dose used in the Phase 2 portion of the study. The primary objective for Cohorts IV-V is to assess the safety and tolerability of the accelerated MT-401 product. For both the Safety Lead-in, which includes Cohorts I and II, and Cohorts III-V, the number of DLTs per cohort will be identified as defined in Section 5.6. The confirmed dose and peptide manufacturer will be identified based on the procedures of the standard 3+3 design described in Section 4.5 and review of entirety of the safety data. Safety endpoints will be analyzed as discussed in Section 9.3.5.

9.3.2. Primary Efficacy Analysis: Group 1

The primary endpoint for Group 1 is RFS, defined as the time between the date of randomization and the date of first relapse per ELN recommendations or death by any cause, whichever occurs first. For patients who remain alive and whose disease has not relapsed, RFS will be censored on the date of last evaluable disease assessment. For patients who remain alive and have no recorded post-randomization disease assessment, RFS will be censored on the date of randomization. Censoring rules for the primary analysis of RFS in Group 1 are presented in Table 9.

Relapse includes either hematologic and/or molecular relapse as defined in Table 6 at any disease assessment.

Confidential Page 52 of 74

For the interim analysis, RFS as determined by the investigator will be used.

Table 9: Censoring Scheme for Primary definition of RFS

Situation	Date of Event or Censoring	Outcome
Relapse per ELN recommendations	Date of first relapse	Event
Death without relapse	Date of death	Event
No baseline disease assessment	Date of randomization	Censored
No on-study disease a ssessments and no death	Date of randomization	Censored
No relapse and no death	Date of last evaluable disease	Censored
	assessment	
New anti-cancer therapy received without relapse	Date of last evaluable disease	Censored
reported prior to or on the same day as disease	assessment on or prior to the date of	
assessment	initiation of subsequent therapy	
Two or more consecutive missed scheduled disease	Date of last evaluable disease	Censored

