6.4.1.2 Primary Efficacy Variables

Phase 2 Adjuvant (Group 1):

- RFS: defined as the time between the date of randomization and the date of first relapse per ELN recommendations or death by any cause, whichever occurs first. Relapse includes either hematologic and/or molecular relapse as defined in [Table 2](#) at any disease assessment. In the event that no relapse or death is documented prior to analysis cutoff or the start of new anti-cancer therapy, RFS will be censored on the date of the last evaluable disease assessment demonstrating no relapse prior to analysis cutoff or the start of new therapy. For patients who remain alive and have no baseline disease assessment or have no post-randomization disease assessment, RFS will be censored on the date of randomization. In addition, if relapse or death occurs after extended time without disease assessments, RFS will be censored on the date of the last evaluable disease assessment prior to the missed disease assessments.

For patients with relapse or death, a variable will be created to flag whether the earlier date of relapse or death occurs after extended time without disease assessments. The extended time is defined as below:

- Time from randomization date to Day 0 visit + 12 weeks + assessment window of 2 weeks, if the latest assessment prior to the event (relapse or death, whichever is earlier) \leq randomization date + 0.5*time from randomization date to Day 0 visit. For patients without Day 0 visit, an artificial Day 0 visit will be derived as randomization date + mean time from randomization date to Day 0 visit date in MT-401 arm, for analysis purpose only.
- 24 weeks + assessment window of 2 weeks, if the latest assessment prior to the event (relapse or death, whichever is earlier) \leq Day 0 visit + 6 weeks & $>$ randomization date + 0.5*time from randomization date to Day 0 visit
- 38 weeks + assessment window of 5 weeks, if the latest assessment prior to the event (relapse or death, whichever is earlier) \leq Day 0 visit + 18 weeks & $>$ Day 0 visit + 6 weeks
- 78 weeks + assessment window of 5 weeks, if the latest assessment prior to the event (relapse or death, whichever is earlier) \leq Day 0 visit + 37 weeks & $>$ Day 0 visit + 18 weeks
- 104 weeks + assessment window of 5 weeks, if the latest assessment prior to the event (relapse or death, whichever is earlier) \leq Day 0 visit + 78 weeks & $>$ Day 0 visit + 37 weeks

Phase 2 Active Disease (Group 2):

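### Group 1 RFS runs from randomization but disease assessments run from Day 0, and no rule keeps the interval between them equal across arms; a systematic difference would bias the hazard ratio toward the arm with the later Day 0

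*Protocol*

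**What the plan says.** **Endpoint clock.** In Protocol Section 9.3.2 the Group 1 primary endpoint, RFS, is "defined as the time between the date of randomization and the date of first relapse per ELN recommendations or death by any cause". SAP Section 6.4.1.2 agrees: "RFS: defined as the time between the date of randomization and the date of first relapse per ELN recommendations". Molecular relapse counts as an event. Event-free patients are censored at their last evaluable disease assessment.

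**Assessment clock.** Protocol Section 1.3, Table 1, places Group 1 disease assessments at Day 0 (unless one was done in the preceding 3 weeks), Weeks 12 and 24 (±1 week), Week 52 (±4 weeks), then yearly. Footnote c says "Timing of Follow-up Visits are in relation to the timing of the Day 0 visit".

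**What Day 0 is.** Footnote c: "Day 0/Week 0 is considered the day of the first infusion of MT-401". For the control arm, footnote d: "Week 0 visit for SoC patients may occur between days 85-130 post-HSCT, as instructed by Sponsor". Footnote c adds: "Sponsor will schedule Day 0 timing for all patients in all groups, including Group 1 SoC arm". Section 5.1 gives adjuvant MT-401 the same range of days 85-130 post-HSCT.

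**Blinding.** Protocol Section 6.3 says "the endpoints are objectively evaluated without the concern for bias, the study is not blinded".

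**SAP handling.** In Section 6.4.1.2 the first missed-assessment limit is the patient's own randomization-to-Day 0 interval plus 12 weeks plus a 2-week window. A patient with no Day 0 visit is given the mean interval of the MT-401 arm. Section 7.4.4 adds a landmark analysis of patients still event-free at Day 0. Section 7.1.5 defines Study Day 0 for Group 1 as the randomization date, which conflicts with Table 1 and with the SAP's own Section 6.4.1.2.

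**The concern.** An arm whose Day 0 falls later after randomization has its Week 12, 24, 52 and yearly assessments later on the RFS clock. Day 0 is also reached differently in the two arms. In Arm A it needs product in hand and the pre-infusion GVHD and steroid criteria to be met. In Arm B it is a visit date that a sponsor aware of the assignment chooses. Objective response criteria do not remove a bias that comes from when patients are examined.

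RFS is the only randomized primary comparison. Molecular relapse is found by testing, and the gaps between assessments after Day 0 grow from 12 to 28 to about 52 weeks, so many event dates could be visit dates. The same hazard ratio feeds the interim analysis at 45 events, where an HR above 1.1 triggers the non-binding futility rule and conditional power of 50-80% triggers expansion (SAP Section 7.4.7.3).

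**Working it through.** **1. The plan's own figure.** Protocol 9.1.1 and SAP 7.6 give 90 events, 80% power, two-sided alpha 0.05 and HR 0.55 (medians 8 and 14.5 months). Schoenfeld: d = 4(1.960 + 0.842)² / (ln 0.55)² = 31.4 / 0.357 ≈ 88. Power at 90 events = Φ(√90/2 × 0.598 − 1.960) = Φ(0.876) = 80.9%. The figure reproduces.

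**2. Not every relapse is dated later.** Take Day 0 at week 2 after randomization in SoC and week 6 in MT-401. Visits then fall at weeks 2, 14, 26 and 6, 18, 30. Within one 12-week cycle:
- onset in weeks 18-26 (8 weeks of onsets) is found at week 26 in SoC and week 30 in MT-401, 4 weeks later;
- onset in weeks 14-18 (4 weeks of onsets) is found at week 26 in SoC and week 18 in MT-401, 8 weeks earlier.

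8 × 4 = 4 × 8, so the mean delay is equal.

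**3. Why the log-rank test still shifts.** Assume for illustration that 40 patients per arm are event-free after the Week 24 visit, with a true median of 8 months (34.8 weeks) in both arms. Relapses found at Week 52 are 40 × (1 − 2^(−28/34.8)) = 17.1 per arm.
- Same day in both arms: expected in MT-401 = 34.2 × 40/80 = 17.1, so O − E = 0.
- SoC seen first: expected in MT-401 = 17.1 × 40/80 + 17.1 × 40/(40 + 22.9) = 8.6 + 10.9 = 19.4, so O − E = 17.1 − 19.4 = −2.3.

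The SoC risk set is already depleted when the MT-401 relapses are counted. In this block the order of the visits matters, not the length of the gap.

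**4. Simulation under no effect.** From the documents: 75 per arm, 50-month uniform accrual, cut at the 90th event, SoC median 8 months, the Table 1 visits and windows, the 3-week exemption at Day 0, and censoring at the last assessment. Assumed: exponential times, randomization at day 85, Day 0 within days 85-130, unstratified log-rank test, and 0%, 25% or 50% of events dated at their true time (deaths or symptomatic relapse). There were 3,000 trials per cell. Entries are apparent HR and the chance of a significant result for MT-401 (nominal 2.5%).

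| Mean difference in Day 0 | 0% prompt | 25% prompt | 50% prompt |
|---|---|---|---|
| None | 1.00, 3.0% | 1.00, 2.9% | 1.00, 2.5% |
| MT-401 later by 15 days, overlapping ranges | 0.88, 8.6% | 0.92, 6.6% | 0.96, 4.1% |
| MT-401 later by about 2 weeks | 0.85, 11.0% | 0.90, 7.1% | 0.94, 4.5% |
| MT-401 later by about 3.5 weeks | 0.83, 13.6% | 0.90, 6.8% | 0.94, 4.8% |
| MT-401 later by about 5.7 weeks | 0.83, 13.7% | 0.89, 8.0% | 0.94, 4.8% |
| SoC later by about 5.7 weeks | 1.21, 0.3% | 1.12, 0.8% | 1.06, 1.2% |

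The 45-day window caps the difference at 45/7 = 6.4 weeks. Separately programmed simulations gave 0.86-0.88 and 9-11% for a 2-week difference with all events visit-dated, and 0.92-0.97 and about 5-6% with 25-50% prompt. A 1-week difference gave 0.94 and 5.1%, or 0.97-0.98 and 3.5-4.3% with prompt dating. With a true HR of 0.55 and all events visit-dated, a 3.5-week difference moved the apparent HR to 0.46.

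**The case against.** A reader might infer that the schedule favours MT-401. The documents do not support that. One party schedules Day 0 for both arms inside the same window and can align them. Donor material is collected separately from the transplant collection or about 30 days after (Protocol 4.1). Manufacture takes over 2 weeks, or about one week with the accelerated process, and the product is then cryopreserved, so it may exist before Day 80. The GVHD and steroid criteria could delay some Arm A patients, but no passage shows a systematic delay.

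A reader might also infer that every MT-401 relapse would be dated later. Step 2 shows otherwise.

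The size is also open to challenge. Clinically prompted assessments are recorded (Table 1 footnote j), and unscheduled efficacy data enter the endpoints (SAP 7.1.2). Blasts in blood count as relapse, and only Arm A has required laboratory visits at Weeks 2 and 4. That opposing influence was not modelled.

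All of this stands, and it makes the bias conditional and its size uncertain. It does not supply the missing rule, because the ability to align the arms is not a requirement to do so. The SAP's missed-assessment limit lengthens with the interval, so it follows a difference and does not correct it. The artificial Day 0 covers only patients without a Day 0 visit. The landmark analysis is additional to the primary analysis, and its time origin is not stated, so it does not clearly correct the problem.

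**Conclusion.** The concern holds as a conditional weakness of the assessment schedule. RFS and its assessments are on different clocks, and nothing keeps the gap between the clocks equal across arms. If the gap differs systematically, the HR and log-rank test are biased toward the arm with the later Day 0, whichever arm that is. With no true effect and an MT-401 Day 0 about 2 weeks later, the apparent HR is about 0.85-0.88 with about 9-11% false wins if all events are visit-dated. With 25-50% of events dated promptly, differences of 2 to 5.7 weeks give about 0.89-0.97 and 4-8%. With equal Day 0 timing there is no bias.

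These sizes rest on exponential times, randomization at day 85 and an assumed share of promptly dated events. The documents give neither that share nor the actual intervals. The effect on the interim HR at 45 events was not calculated. The matter should be settled before the comparison is read, because the correction is cheap.

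**What to change.** 1. In Table 1 footnotes c and d, put Group 1 disease assessments on one clock in both arms. Either time them at fixed weeks from randomization, leaving infusions and safety visits on Day 0, or require the SoC Day 0 to match the MT-401 randomization-to-Day 0 interval.
2. Rewrite the missed-assessment intervals in SAP 6.4.1.2 on that clock. With randomization timing, the artificial Day 0 is no longer needed. Reconcile the Study Day 0 definition in SAP 7.1.5.
3. Add an interval-censored proportional-hazards sensitivity analysis of RFS, which also covers patients already assessed under the present schedule.
4. Report time from randomization to Day 0 and to each assessment, by arm.

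The cost is a footnote amendment and SAP text; the number of scheduled assessments need not change. Randomization timing removes the problem fully but can bring Arm A assessments close to infusions. With randomization at day 85 and Day 0 at day 130 (week 6.4), a third infusion falls at week 10.4, which is 1.6 weeks before a Week 12 assessment. That must be reconciled with the 2-week visit spacing in footnote c. Matching the SoC Day 0 avoids this conflict, but it works only as far as the actual intervals in the two arms agree, so the by-arm report is needed to confirm it.

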9.3.4.2. Graft-versus-host Disease- and Relapse-free Survival (Groups 1 and 2)

Graft-versus-host disease- and relapse-free survival (GRFS) is defined as the time from randomization (Group 1) or first dose (Group 2) to date of GVHD, relapse, or death, whichever occurs first. GVHD events are defined as any grade 3-4 acute GVHD or chronic GVHD requiring systemic therapy. A patient who has not experienced any of these events will be censored on the date of their last evaluable disease

Confidential Page 54 of 74

assessment. For patients who remain alive and have no recorded post-baseline disease assessment, GRFS will be censored on the date of randomization (Group 1) or first dose (Group 2). Censoring rules for the analysis of GRFS in Group 1 are presented in Table 11.

Table 11. Censoring Scheme for Primary Definition of GRFS

Situation	Date of Event or Censoring	Outcome
GVHD or relapse	Date of first event type	Event
Death without GVHD or relapse	Date of death	Event
No baseline disease assessment	Date of randomization	Censored
No on-study disease assessments and no death	Date of randomization	Censored
No GVHD, no relapse, and no death	Date of last evaluable disease	Censored
	assessment	
New anti-cancer therapy received without relapse	Date of last evaluable disease	Censored
reported prior to or on the same day as disease	assessment on or prior to the date of	
assessment	initiation of subsequent therapy	
Two or more consecutive missed scheduled disease	Date of last evaluable disease	Censored
assessments	assessment prior to the missed disease	
	assessments	

Abbreviations: AML=acute myeloid leukemia; GRFS=graft-versus-host disease relapse-free survival

The statistical methods for analyzing GRFS are identical to those described for RFS.

GRFS will be summarized for Group 1 and Group 2 Subgroup D, respectively.

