9.3.5. Safety Analyses

Safety and toxicity outcomes including treatment-emergent AEs, CRS, GVHD, neurological findings, and laboratory evaluations will be summarized using descriptive statistics for all patients in the All treated population by group. Safety evaluations will be based on the incidence, intensity, and type of AEs or SAEs, as well as changes in the patient's physical examination findings, vital signs, and clinical laboratory results.

AEs will be assessed for severity according to the U.S. NCI CTCAE, Version 5.0, and the verbatim AE terms will be coded using the Medical Dictionary for Regulatory Activities (MedDRA Version 25 or higher) for purposes of summarization.

The safety analysis will be performed in all treated patients. Descriptive statistics of safety will be presented by dose cohort or by treatment arm. All on-treatment AEs, drug-related AEs, late-emergent drug-related AEs, SAEs and drug-related SAEs will be tabulated using worst grade per NCI CTCAE Version 5.0 criteria by system organ class and preferred term. On-study laboratory parameters including hematology, chemistry, liver function and renal function will be summarized using worst grade per NCI CTCAE Version 5.0 criteria.

All deaths within 30 and 60 days of the last dose of MT-401 will be summarized. For Group 1 SoC arm, deaths within 30 days and 60 days of randomization date plus average time from randomization to last dose in the MT-401 arm will also be summarized as reference.

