7.5.5.3 GVHD Assessments

Shift from baseline in maximum overall grade for chronic GVHD will be summarized at each post-baseline visit and worst case post-baseline, and will include the count and percentage of patients within each shift category and treatment group.

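### Up to Week 12, Arm B has one required GVHD and AE examination after Day 0 against three in Arm A, and the SAP has no stand-alone by-arm summary of acute GVHD

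*Protocol*

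**What the plan says.** Table 1 in Protocol 1.3 has a row for "GVHD Assessments" marked at Baseline, Weeks 0, 2, 4, 12, 24 and 52, then yearly. The row for "AE, SAE, and concomitant medication review" is marked at Baseline and Weeks 0, 2 and 4, and then continues. Footnote d relaxes this for the control arm: "SoC patients do not need to perform visit Weeks 2 or 4, unless clinically indicated". Arm B keeps its Week 0 visit. The footnote on study treatment says "Group 1- Arm B (SoC) patients will continue to follow the SoA minus administration of MT-401" and does not mention the exemption.

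AE collection is continuous over the same period: "All AEs and SAEs, from Day 0 and Baseline, respectively, to the Week 12 Visit will be collected". After Week 12, only treatment-related events are collected.

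On analysis, Protocol 9.3.5 states: "Safety and toxicity outcomes including treatment-emergent AEs, CRS, GVHD, neurological findings, and laboratory evaluations will be summarized", with safety shown by dose cohort or arm. Protocol 8.2.1 has GVHD assessed under both acute and chronic guidelines. The GVHD section of the SAP, 7.5.5.3, reads: "Shift from baseline in maximum overall grade for chronic GVHD will be summarized at each post-baseline visit and worst case post-baseline", by treatment group. SAP 7.7 reports no departures from the protocol.

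**The concern.** GVHD is the toxicity that Protocol 8.2.1 names for allogeneic T cells, and GVHD assessment is a secondary safety endpoint in Protocol Table 3. Group 1 is the only randomized comparison in the study. If one arm is examined more often during the dosing weeks, it will tend to show more findings, and earlier ones, even when the underlying risk is equal. A worst-grade table is sensitive to this because it takes the maximum over all looks.

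The second issue is independent of the first. A reader of the study report would expect the maximum acute GVHD grade by arm. The SAP as written does not produce it.

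**Working it through.** The plan states no figure on this point, so there is none to reproduce. The check has three steps.

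**1. Count the looks.** Inputs: the GVHD row of Table 1, with footnote d applied to Arm B.

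| | Arm A | Arm B |
|---|---|---|
| Baseline through Week 12 | 5 (Baseline, 0, 2, 4, 12) | 3 (Baseline, 0, 12) |
| After Day 0 through Week 12 | 3 | 1 |
| After Day 0 through Week 52 | 5 | 3 |
| Longest gap, Weeks 0-12 | 8 weeks | 12 weeks |

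**2. Illustrate what unequal looks can do.** Assumptions, none of them from the documents: onset is uniform over Weeks 0-12, an episode lasts d weeks, and it is found only if present at a required visit after Day 0.

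- Arm B (Week 12): the share found is d/12 for d up to 12.
- Arm A (Weeks 2, 4, 12): the share is 3d/12 for d up to 2, and (4 + d)/12 for d from 2 to 8. In the second case, Weeks 2 and 4 together catch every onset in the first 4 weeks.

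| Duration d | Arm A | Arm B |
|---|---|---|
| 1 week | 3/12 = 25% | 1/12 = 8% |
| 2 weeks | 6/12 = 50% | 2/12 = 17% |
| 4 weeks | 8/12 = 67% | 4/12 = 33% |
| 6 weeks | 10/12 = 83% | 6/12 = 50% |
| 8 weeks | 12/12 = 100% | 8/12 = 67% |
| 12 weeks or more | 100% | 100% |

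The mean wait from onset to the next required visit is (2²/2 + 2²/2 + 8²/2)/12 = 36/12 = 3.0 weeks in Arm A and (12²/2)/12 = 6.0 weeks in Arm B.

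**3. Trace where acute GVHD appears by arm.**

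- SAP 7.5.5.3: chronic GVHD only.
- SAP 7.5.2: TEAE tables by treatment group, preferred term and CTCAE grade. Acute GVHD appears if reported as an AE, but not under the guideline grading of Protocol 8.2.1. SAP 7.1.5 starts the TEAE period at first dose in Arm A and at randomization in Arm B.
- GRFS (Protocol 9.3.4.2): "GVHD events are defined as any grade 3-4 acute GVHD or chronic GVHD requiring systemic therapy". Grade 2 acute GVHD does not count, and GVHD is merged with relapse and death. SAP 7.4.7.5 makes GRFS descriptive.
- SAP 7.4.2: maximum acute GVHD grade is summarized as baseline history. It has no post-baseline counterpart.

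**The case against.** The case for leaving the plan alone has real weight.

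- The exemption is not absolute. Symptomatic Arm B patients can be seen. The note to Table 1 has unscheduled visits follow the Week 24 column, which includes GVHD assessment, and SAP 7.1.2 lets unscheduled data count toward the worst post-baseline value. AEs are collected continuously to Week 12 in both arms, so an episode that resolves between visits can still be reported. This stands. It narrows the gap and confines it mainly to mild, short or unreported disease.
- A reader might infer that acute GVHD is not compared by arm at all. The documents do not support that. Grade 3-4 acute GVHD enters GRFS, which is compared between arms by the RFS methods, and AE-reported acute GVHD enters the TEAE tables. Neither output, however, gives guideline-graded acute GVHD by arm.
- A reader might also infer that GRFS times are driven by the visit schedule. GRFS uses the date of GVHD, not a visit date, and its events are severe or treated disease that is likely to surface clinically.
- SoC safety data are shown only for reference (Protocol Table 8), and extra looks in Arm A cannot manufacture a benefit for MT-401. Both points stand and limit the importance of this finding.
- Another asymmetry runs the other way. Under SAP 7.1.5, the TEAE period and the safety baseline in Arm B run from randomization, so a Week 0 finding in Arm B can count as post-baseline. The net direction in the AE tables is therefore not settled. This supports a common window rather than no change.

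**Conclusion.** The point holds in two parts.

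First, required surveillance after Day 0 through Week 12 is 3 examinations in Arm A and 1 in Arm B. The schedule alone pushes by-arm worst-grade GVHD and AE summaries against MT-401, chiefly for mild or short events. The shares in the working, such as 50% against 17% for a 2-week episode, should not be read as an estimate of bias. They rest on assumed onset and duration, ignore unscheduled visits and retrospective reporting, and are an upper bound on the imbalance under those assumptions. At 12 weeks' duration or more the gap vanishes.

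Second, the SAP has no stand-alone by-arm summary of post-baseline acute GVHD. That falls short of Protocol 9.3.5 and does not fit the SAP 7.7 statement that nothing changed.

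Required disease-assessment weeks are the same in both arms, so the primary RFS comparison is not touched by this point, and no sample size or power figure changes.

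**What to change.** In SAP 7.5.5.3:

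- Add a by-arm summary of maximum post-baseline acute GVHD grade, with the incidence of Grade 2-4 and Grade 3-4. Use the guideline grading cited in Protocol 8.2.1, over a window with the same start and end in both arms.
- Keep the all-visit worst-grade tables.
- Add a sensitivity version for acute and chronic GVHD that leaves out Arm A's scheduled Week 2 and 4 assessments, and show those findings separately.

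The cost is a few extra tables from data already scheduled for collection. The common-visit version omits early Arm A findings made during dosing, so it must supplement the all-visit table and not replace it. Telephone contacts with Arm B at Weeks 2 and 4 would even out ascertainment at source, but they are optional and the fix does not depend on them.
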